Informed consent 32 Model consent form and other related documentation given materials to participants and authorised surrogates The only documentation generated will be educational material and SIGHT provider prompted messages for providers. All, material has undergone an internal review and will be approved by the clinical directors and the VUMC IRB before implementations of the SIGHT study. 33 Plans for collection, laboratory evaluation, and storage of Biological biological specimens for genetic or molecular analysis in specimens the current trial and for future use in ancillary studies, if applicable No specimens will be collected by the study team or stored for future use. All, study related data will be collected via the electronic health record by following patients being seen at VUMC via usual care.

Data datagory	inionation			
Primary registry and trial identifying number	ClinicalTrials.gov – NCT06744543			
Date of registration in primary registry	**11 February, 2025**			
Secondary identifying numbers	NA			
Source(s) of monetary or material support	No funding source			
Primary sponsor	NA			
Secondary sponsor(s)	NA			
Contact for public queries	[name] [contact]			
Contact for scientific queries	[name] [contact] Vanderbilt University Medical Center Department of Medicine, Division of Genetic Medicine, Nashville TN Center for Digital Genomic Medicine Vanderbilt Genetics Institute			
Public title	Clinical Decision Support to Find Individuals at Risk of Genetics Disease			
Scientific title	Integrating Machine Learning into Clinic: Systematic Identification of Genetic Health Testing (SIGHT) Randomized control trial.			
Countries of recruitment	United States			
Health condition(s) or problem(s) studied	Genetics Disease in the Pediatric Population			
Intervention(s)	Active comparator: Patients having a SIGHT predicted score greater than equal to 0.30 with a score less than 0.30 seen in the POD-C pediatric primary care clinic at the Vanderbilt University Medical Center (VUMC) One Hundred Oaks location (OHO .			
	Controls: Randomized pediatric patients who meet criteria without intervention seen at POD-C pediatric primary care clinic at the Vanderbilt University Medical Center (VUMC) One Hundred Oaks location (OHO)			
Key inclusion and exclusion criteria	Ages eligible for study: >1 years and < 20 years of age Sexes eligible for study: both			
	Inclusion criteria: Inclusion criteria will consist of patients > 1 year old, < 20 years of age with a visit to POD-C pediatric primary care clinic at the Vanderbilt University Medical Center (VUMC) One Hundred Oaks location (OHO).			
	Exclusion criteria: Exclusion criteria will consist of patients who have been programmatically excluded due to having already received a chromosomal microarray at VUMC, and patients > 20 years of age.			
	Interventional			
Study type	Allocation: Randomized intervention model.			
Date of first enrolment	February 2025			
Target sample size	1000			
Recruitment status	Recruiting			
Primary outcome(s)	Number of cases diagnosed via a Chromosomal Microarray compared to the controls			

Information

Data category

Data category Info	Information		
Key secondary outcomes	 Time to patients receiving genetic testing Rate of genetic testing Satisfaction of physicians who received a SIGHT prompted provider message Number of patients receiving a diagnosis via any test (molecular confirmation), or a clinical diagnosis by a pediatric geneticist following the course of usual care. 		

*It is strongly recommend ed that this checklist be read in conjunction with the SPIRIT

2013 Explanation & Elaboration for important clarification on the items. Amendments to the protocol should be tracked and dated. The SPIRIT checklist is copyrighted by the SPIRIT Group under the Creative Commons "Attribution-NonCommercial-NoDerivs 3.0 Unported" license.

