Healthcare providers of the patients in the SIGHT-guided intervention arm will receive alert messages, recommending consideration of genetic testing and referral to the genetics clinic. In contrast, providers of the patients in the standard care arm will not receive such alerts and will proceed with usual care practices. Patients with a score greater than equal to 0.30 and who have a scheduled visit at POD-C will be randomized in a 1:1 ratio to either the usual care or SIGHT-guided arm. Randomization will be stratified within the VUMC pediatric POD-C clinic. Patients will be excluded if they have already undergone Chromosomal Microarray testing at VUMC.

Objectives 7 Specific objectives or hypotheses

This study will evaluate the effectiveness of SIGHT as a clinical support system to prompt provider/patient discussion and shared decision making regarding the need for genetic testing in form of a chromosomal microarray. We seek to study if identifying patients with high SIGHT scores will decrease the duration of time to testing and increase diagnostic yield. SIGHT only relies on data already collected in routine clinical encounters and is calculated prior to a clinical visit at VUMC.

SIGHT does not replace clinical judgment in determining the necessity for genetic testing, but we seek to measure whether SIGHT increases the rates at which the important problem of elucidating the genetic etiology of disease is addressed. Our SIGHT-guided intervention group will be patients with high SIGHT scores where their provider receives a clinical communication recommending ordering of a genetic test and referral to the genetics clinic. Our comparison group will be patients with equivalently high SIGHT scores that receive usual care (i.e., do not receive a provider message). Patients will be from the POD-C pediatric primary care clinic at the Vanderbilt University Medical Center (VUMC) One Hundred Oaks location (OHO).

Trial design

8

Description of trial design including type of trial (eg, parallel group, crossover, factorial, single group), allocation ratio, and framework (eg, superiority, equivalence, noninferiority, exploratory)

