Analysis Metric: Time to event, measured from the initial patient visit to the time genetic testing is conducted.

Method of Aggregation: Median time in days

Specific Measurement Variable: Rates of genetic testing. **Analysis Metric:** Proportion of patients who received testing **Method of Aggregation:** Proportion of patients, presented as a percentage

Time Point: Assessed after one year to include enough time for patients to undergo testing through the usual course of care.

Specific Measurement Variable: Diagnosis via any genetic testing.

Analysis Metric: Proportion of patients diagnosed with a genetic disease following molecular testing or clinical evaluation. **Method of Aggregation:** Proportion of patients, presented as a percentage.

Time Point: Assessed after one year to include enough time for patients to undergo additional testing through usual care.

Specific Measurement Variable: Adherence to the SIGHT-prompted provider message.

Analysis Metric: Frequency of provider actions via referral to genetics and ordering a patient CMA following receipt of a SIGHT-prompted message.

Method of Aggregation: Proportion of instances where the provider follows the SIGHT recommendation.

Time Point: Information will be collected at the end of the study.

Participant timeline

- Time schedule of enrolment, interventions (including any run-ins and washouts), assessments, and visits for participants. A schematic diagram is highly recommended (see Figure)
 - 1. Enrollment Process: Eligibility Screening: Conducted at the initial patient visit. Consent Process: Following eligibility screening, informed consent will not be obtained as patients are following usual care.
 - **2. Interventions:** SIGHT-Prompted Provider Message: Initiated following screening for patients who meet the predefined risk threshold.
 - 3. Assessments: Baseline Assessment: Conducted during the initial visit, including collection of patient health data. Follow-up Assessments: Scheduled after initial visit to monitor the outcomes, such as number of patients receiving a diagnosis, time to genetic testing, and diagnostic yield.
 - 4. Visits: Initial Visit: SIGHT prompted provider message followed by review of referrals and documentation attributable to the initial patient visit. Subsequent Visits: Regular follow-ups as per usual pediatric care, during which recommendations and any genetic testing decisions are documented and assessed.

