 - **5. Study Close-Out:** Final Assessment: Conducted at the end of the study period to collect the final data on all outcomes.

Sample size

14 Estimated number of participants needed to achieve study objectives and how it was determined, including clinical and statistical assumptions supporting any sample size calculations

Previous data suggest that, under the usual course of care, 9% of high-risk patients (those with a predicted score of ≥ 0.3) had genetic testing. Of those, 9% received a genetic diagnosis, resulting in a genetic diagnosis rate of 0.81% (0.09*0.09) among high-risk patients

One thousand high-risk patients (score \geq 0.3) will be randomized 1:1 (500 per arm). This sample size provides 80% power to detect an increase in the genetic diagnosis rate from 0.81% under standard care to at least 3.6% with the SIGHT intervention (chi-square test, α =0.05)

Recruitment 15 Strategies for achieving adequate participant enrolment to reach target sample size

The VUMC POD-C pediatric clinic has had over 200,000 patient encounters from over the last five years with more than 30,000 unique patients and over 10,000 unique patients in 2023. The clinic averages 144 visits per day (median = 165). Estimates indicate potentially 1-2 patients flagged per day which should readily provide enough patients for an adequate sample size over a two to three-year period.

Methods: Assignment of interventions (for controlled trials)

Allocation: Sequence generation 16a

Method of generating the allocation sequence (eg, computer-generated random numbers), and list of any factors for stratification. To reduce predictability of a random sequence, details of any planned restriction (eg, blocking) should be provided in a separate document that is unavailable to those who enrol participants or assign interventions.

The SIGHT study will utilize a computer-generated assignment schedule for all patients seen in the POD-C pediatric clinic with a score greater than or equal to 0.3 for allocation into the intervention group. A computer-generated randomization schedule will be used for assigning participants to the control group. This is completed using the built-in random module of python, assigning patients with equal scores either 0 (control) or 1 (intervention) to each patient who has met all previously defined criteria, with assignments saved to a log file.

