The allocation will be done with a 1:1 ratio. This randomization process is designed to ensure that patients surpassing a previously defined threshold for predicted risk of needing genetic testing are randomly selected for the intervention group. A SIGHT-prompted provider message will be generated for patients in the intervention group, while patients in the control group will receive usual care without this prompted message.

Patients who exceed a predefined risk threshold and are scheduled for their first visit within a year will be eligible for randomization to the intervention group. An estimated 500 patients will be randomly selected to receive a SIGHT-prompted provider message as part of the intervention.

The comparator arm will consist of the random eligible patients who do not receive the intervention. These patients will not be a typical control group to avoid ethical concerns related to withholding potentially important care but will follow usual care and may still get genetic testing.

To maintain the integrity of the randomization process, the study will employ random allocation to intervention and comparator arms with the expectation of a 1:1 ratio over time.

This method of randomization aligns with ethical standards and the goal of the study to evaluate the effectiveness of the SIGHT intervention while ensuring that all patients receive the usual care appropriate to their clinical needs. Allocation concealment mechanism

Mechanism of implementing the allocation sequence (eg, central telephone; sequentially numbered, opaque, sealed envelopes), describing any steps to conceal the sequence until interventions are assigned.

The allocation sequence will be implemented using a secure, computerized system to ensure allocation concealment. This system will generate the allocation sequence and assign patients who surpass the predefined risk threshold to either the intervention or the comparator group.

The allocation system will maintain concealment by ensuring that randomization is not processed until a patient has been identified as eligible. This process occurs after the patient's eligibility is confirmed but before any intervention is assigned, to prevent selection bias and to maintain the integrity of the randomization process.

Implementation 16c

Who will generate the allocation sequence, who will enrol participants, and who will assign participants to interventions

Allocation Sequence Generation

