The statistical analysis will utilize a chi-square test for binary outcomes such as the presence or absence of a genetic diagnosis as identified by the test or provider adherence to SIGHT message recommendations. For continuous secondary outcomes, such as the time to genetic testing, a T-test or Mann-Whitney U test will be used depending on data distribution. Subgroup analyses will involve regression methods to assess the differential effects of the intervention across subgroups defined by baseline demographic characteristics (e.g. age, sex, race). Multivariate analyses will be conducted using logistic regression for binary outcomes and linear or Cox proportional hazards regression for continuous or time-to-event outcomes, respectively. Model assumptions will be checked through the assessment of residuals and model fit will be evaluated accordingly.

When indicated, a two-sided p-value of less than 0.05 will be considered statistically significant. The Bonferroni correction will be applied to account for multiple comparisons when analyzing multiple outcomes. R will be used to perform all analyses. The analysis plan will follow the intention-to-treat principle, with all randomized participants included in the analysis according to the group to which they were allocated.

Variable/outcome	Hypothesis	Outcome measure	Methods of analysis
Primary			R will be used to perform all analysis.
Number of diagnoses via CMA	More patients are diagnosed being flagged by SIGHT via a Chromosomal Microarray	Number of patients flagged by SIGHT who receive a diagnosis via CMA over one year vs controls [binary]	Chi-square test
Secondary			
a. Time to genetic test	Patients in the intervention arm will receive genetic testing faster than those in the controlarm.	Duration in days for which patients flagged by SIGHT receive a genetic test vs control [continuous]	Cox proportional Hazards to compare the time to event (in this case genetic testing) between two groups while controlling for covariates.
b. Rates of genetic testing	Increased rates of genetic testing in the intervention arm	Rates of genetic testing ordered by providers between cases and controls over a one-year period after POD-C visit [continuous'	Binary logistic regression to calculate the odds ratio for the likelihood of receiving a genetic test in the intervention arm compared to the controls

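### Randomisation is called stratified, but there is one clinic, no named factor and a per-patient 0/1 draw; separately, the testing-rate model could prespecify the SIGHT score as a covariate

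*Protocol*

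**What the plan says.** Item 6b of the Protocol states "Randomization will be stratified within the VUMC pediatric POD-C clinic". Item 7 fixes a single site: "Patients will be from the POD-C pediatric primary care clinic at the Vanderbilt University Medical Center (VUMC) One Hundred Oaks location (OHO".

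The heading of item 16a asks for stratification factors. The answer names none and gives the mechanism: "This is completed using the built-in random module of python, assigning patients with equal scores either 0 (control) or 1 (intervention) to each patient". The same item says that allocation proceeds "with the expectation of a 1:1 ratio over time". Item 14 plans that 1,000 patients "will be randomized 1:1 (500 per arm".

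In the item 20a table, row b (rates of genetic testing) is specified as "Binary logistic regression to calculate the odds ratio for the likelihood of receiving a genetic test", intervention against control, with no covariate mentioned. Row a (time to test, Cox model) and row d (adherence) each adjust for covariates that are not named. The primary outcome is compared by an unadjusted chi-square test. Age, sex and race are named only as examples of subgroup variables. The SIGHT score is named nowhere as a balancing factor or a covariate.

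**The concern.** A reader of item 6b will assume that the design balances the arms on something. Items 7 and 16a show nothing for it to balance on. If the claim is carried into the trial report, it describes a design that was not used, and an analyst might look for a stratum term that does not exist.

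The words about *equal scores* in item 16a add to the doubt. Read together with the word stratified, they could suggest matching on the SIGHT score. The only shared feature that the protocol describes is the entry threshold of 0.3. If matching is meant, it changes both the randomisation and the analysis; if not, the phrase misleads.

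The second part is an opportunity rather than an error. The score decides entry, is presented in item 6a as a validated predictor, and is computed before the visit. It is a natural covariate for the testing-rate model, and row b does not use it.

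**Working it through.** **1. The statements side by side.** Strata formed by clinic = number of clinics = 1. Item 16a gives no other factor and no block size, and claims 1:1 only as an expectation. Together these describe simple randomisation.

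**2. The plan's own sample size.** Inputs from item 14: 0.81% versus 3.6%, α = 0.05 (two-sided, item 20a), 80% power.
- Mean rate = 0.02205; difference d = 0.0279.
- Uncorrected n = [1.96·√(2·0.02205·0.97795) + 0.8416·√(0.0081·0.9919 + 0.036·0.964)]² / d² = (0.4070 + 0.1740)² / 0.000778 ≈ 434 per arm.
- With continuity correction, n' = (n/4)·[1 + √(1 + 4/(n·d))]² ≈ 503 per arm.

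The planned 500 per arm therefore reproduces as a continuity-corrected chi-square calculation. Nothing in it depends on stratification.

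**3. What a simple draw leaves to chance.**
- Arm size: SD = √1000/2 = 15.8, giving a 95% range of 469 to 531. By the uncorrected formula, power is 84.7% to 85.6% at those extremes, against 85.3% at 500/500.
- Standardised difference in mean score: SD = 2/√1000 = 0.063, giving a 95% range of about ±0.12 SD.

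**4. Primary outcome.** The score's prognostic strength is not in the documents, so it is assumed (1,500 simulated trials per setting).

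| Assumed odds ratio per SD | Unadjusted power | Score-adjusted power | Type I error, unadjusted |
|---|---|---|---|
| 1.0 | 89.3% | 89.7% | 4.7% |
| 1.5 | 90.2% | 90.9% | 5.2% |
| 2.0 | 88.3% | 89.2% | 5.8% |

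The simulation error of the type I rates is about 0.6 points. The power gain is under 1 point throughout. It is already 0.4 points when the score predicts nothing, because the adjusted analysis uses a likelihood-ratio test. There is no case for changing the primary test.

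**5. Row b, testing rates.** The usual-care rate of 9% is from item 14. The 15% and the odds ratios per SD are assumptions.

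Unadjusted power by formula, 500 per arm: [0.06 − 1.96·√(2·0.12·0.88/500)] / √((0.09·0.91 + 0.15·0.85)/500) = (0.0600 − 0.0403)/0.0205 = 0.96, or about 83%.

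Simulated trials of 1,000 patients, arm alone versus arm plus score:

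| Odds ratio per SD | 3,000 trials | 4,000 trials (separate run) |
|---|---|---|
| 1.5 | 83.0% to 83.7% | 82.9% to 83.6% |
| 2 | 83.6% to 85.3% | 84.4% to 86.3% |
| 3 | 83.3% to 88.3% | 84.0% to 88.4% |

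The gain is about 1, 2 and 4 to 5 points.

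**6. Where the gain comes from.** The mean standard error of the log odds ratio rises with adjustment, from 0.202 to 0.204, 0.208 and 0.216. At an odds ratio of 3 per SD the mean log odds ratio moves from 0.575 to 0.655. The ratio of estimate to standard error goes from 0.575/0.202 = 2.85 to 0.655/0.216 = 3.03. Power rises because the adjusted odds ratio is conditional on the score and lies further from 1.

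**7. The effect implied by the plan.** If the yield among those tested stays at 9%, a 3.6% diagnosis rate needs 0.036/0.09 = 40% tested. For 9% versus 40%, z = 0.31/√((0.09·0.91 + 0.40·0.60)/500) = 0.31/0.0254 = 12.2. Unadjusted power is then essentially 100%, and adjustment can add none.

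**The case against.** The strongest reply is that only one word is wrong. Simple randomisation is valid and balances the score in expectation. With 1,000 patients, all at or above the threshold, chance imbalance is small. That stands.

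Covariate lists are commonly left to a statistical analysis plan, and none is shown here. Row a already adjusts for covariates, and item 20a foresees multivariable logistic models in general terms. This also stands: the missing list in row a is no fault, and the score is offered as an improvement to row b as written.

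Several stronger readings are tempting, but the documents do not support them:
- *The draw is certainly unrestricted.* This is a strong inference, not a stated fact. The template wording of item 16a places blocking details in a separate document, although the trial's answer refers to none, and the phrase on equal scores is ambiguous.
- *Adjustment buys precision at no cost.* In the logistic model the standard error rises and the odds ratio changes meaning.
- *The analysis would adjust for data that the message can alter.* Item 13 does say "Baseline Assessment: Conducted during the initial visit, including collection of patient health data". However, no section plans to adjust for health data recorded at the visit. Item 18a takes baseline data from record queries, and item 27 describes a nightly job on stored billing codes. Item 13 also places the message after screening, so the order of message and data collection is not settled.

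**Conclusion.** The contradiction is real and minor. Item 6b claims a stratification that items 7 and 16a do not provide. Correcting it changes no number in the plan: power moves by less than 1 point through unequal arms, and type I error stays near 5%.

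The score covariate in row b is a modest, optional improvement. It is worth about 1 to 5 points of power under an assumed 9% versus 15% tested and assumed odds ratios of 1.5 to 3 per SD. The upper end needs a strong predictor among patients already selected for a high score, and the documents give no evidence on that. If testing rises to about 40%, the gain in power is nil. A reader might infer that the randomisation or the primary comparison is compromised; neither is.

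**What to change.** - **Items 6b and 16a.** Reconcile them. If the draw is simple, delete the stratification claim and say that allocation is a simple 1:1 draw. If a factor or blocks are used, name the factor and method. In item 16a, say what *equal scores* means; if it only means that all patients meet the 0.3 threshold, say that.
- **Row b.** Add the continuous SIGHT score computed at randomisation as a prespecified covariate. Because the odds ratio then becomes conditional on the score, report the unadjusted testing proportions in each arm and their difference beside it. Item 12 already defines this outcome as a proportion.
- **Row a.** Include the same score term among the Cox covariates.
- **Primary outcome.** Leave the chi-square test unadjusted.

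The cost is a few sentences and one term in each of two models. The running allocation does not change. One practical check is needed: item 16a says only that assignments are saved to the log file, so confirm that the score at randomisation is stored with them. Since recruitment is under way, record the covariate choice before outcomes are examined by arm.
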